2.3. Study Plan

Study assessments and procedures are presented by study period and visit in [Appendix 10.1 Table 1](#) and [Table 2](#). A schedule for follow-up on TJR surgery during the study is presented in [Appendix 10.1 Table 3](#).

3. ANALYSIS POPULATIONS

In accordance with guidance from the International Conference of Harmonization of Technical Requirements for Registration of Pharmaceuticals for Human Use (ICH) guideline ICH E9 Statistical Principles for Clinical Trials (1998), the following population of analysis will be used for all statistical analysis:

3.1. The Modified Intent to Treat Set (mITT)

The modified intent to treat set (mITT) includes all randomized patients per IVRS who received at least one dose of study drug based on the treatment allocated (as randomized) including data up to 5 weeks after the last dose of study drug.

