Patients will be instructed to stop using all prohibited medications at the pre-randomization visit. Patients will receive paracetamol/acetaminophen to be used as study-provided rescue medication. In the event of inadequate LBP relief, paracetamol/acetaminophen may be taken as needed, according to local standard of care, to a maximum total dose of 2600 mg (325 mg x 8) per day in North America and 2500 mg (500 mg x 5) per day in Europe, starting at the pre-randomization visit through week 16.

Patients must have a mean daily LBPI NRS score ≥ 4 during the pre-randomization period, in order to be eligible for study participation. Patients may not use paracetamol/acetaminophen for 48 hours prior to the start of a scheduled study visit or during a study visit, in order to minimize the confounding effects of rescue medication on efficacy measures.

Confirmation that there are no exclusionary findings on lumbar MRIs, any hip or knee MRI of joints with a K-L score ≥ 3 , or any other joint on which an MRI was performed during screening must be received before a patient can be randomized.

- **Treatment Period (day 1 through week 16):** The treatment period will begin at the randomization visit (baseline/day 1) and continue through the week 16 visit. Patients who meet study entry criteria will be randomized and will undergo baseline assessments at the day 1 visit. For patients randomized to SC administration, a loading dose equivalent to 2 times the maintenance dose will be administered on day 1.

Patients randomized to 6 mg or 9 mg fasinumab SC Q4W and placebo IV 9 mg Q8W will receive 2 SC injections of fasinumab on day 1 (SC loading dose), 1 SC injection at weeks 4, 8, and 12, and 1 IV infusion of matching placebo on day 1 and at week 8.

Patients randomized to 9 mg fasinumab IV Q8W and placebo SC Q4W will receive 1 IV infusion of fasinumab on day 1 and at week 8, 2 SC injections of matching placebo on day 1 (placebo for SC loading dose) and 1 SC injection of matching placebo at weeks 4, 8, and 12.

Patients randomized to placebo SC Q4W and placebo 9 mg IV Q8W will receive 2 SC injections of matching placebo to fasinumab on day 1 (SC loading dose), 1 SC injection of matching placebo at weeks 4, 8, and 12, and 1 IV infusion of matching placebo on day 1 and at week 8.

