Study drug (fasinumab or placebo) will be administered at the study site. Patients will be observed in the clinic for approximately 2 hours after IV administration of study drug and for 1 hour after SC dosing for evidence of a hypersensitivity reaction.

Paracetamol/acetaminophen may be taken as rescue medication in the event of inadequate LBP relief, as described previously. The use of paracetamol/acetaminophen is prohibited for 48 hours prior to the start of each scheduled study visit in order to minimize the confounding effects of rescue medication on study measures.

[figure not shown]
Every day, patients will report their LBPI scores using the NRS and their daily use of rescue medication for LBP in the EDiary.

Efficacy and safety assessments will be performed as outlined in [Table 1](#). Potential events of adjudicated arthropathy will be monitored via clinical signs and symptoms of worsening joint pain during the study (eg, using the joint pain questionnaire and imaging). Potential events of sympathetic nervous system dysfunction will be monitored throughout the study via the Survey of Autonomic Symptoms.

- **Follow-up Period (week 20 through week 36 visits):** The follow-up period starts after the week 16 visit and continues through the week 36 visit.

During the follow-up period, safety and efficacy assessments will be performed as outlined in [Table 2](#). Potential events of adjudicated arthropathy and sympathetic nervous dysfunction will be monitored as described previously.

Figure 1: Study Flow Diagram

A comprehensive risk management approach will be implemented for 3 adverse events of special interest (AESI), adjudicated arthropathy, joint replacement, and sympathetic nervous system dysfunction; this approach is discussed in [Section 7.4.1](#).

In order to monitor for outcomes for potential cases of adjudicated arthropathy, if a patient must undergo total joint replacement (TJR) surgery during the study, they will be asked to complete an early termination visit prior to the surgery if at all possible and to return for post-surgery follow-up as outlined in [Table 3](#).

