5. STUDY TREATMENTS

5.1. Investigational Treatment

Patients will be randomized to 1 of the following 4 treatment groups:

1. Fasinumab 6 mg SC Q4W and placebo 9 mg IV Q8W
2. Fasinumab 9 mg SC Q4W and placebo 9 mg IV Q8W
3. Fasinumab 9 mg IV Q8W and placebo SC Q4W
4. Placebo SC Q4W and placebo 9 mg IV Q8W

Patients randomized to treatment groups 1 or 2 (6 mg or 9 mg fasinumab) will receive SC injections of fasinumab on day 1, and at weeks 4, 8, and 12 for a total of 4 doses. These patients will also receive matching placebo IV on day 1 and at week 8. For patients randomized to SC administration, a loading dose equivalent to 2 times the maintenance dose will be administered SC on day 1.

Patients randomized to treatment groups 3 or 4 will receive matching placebo to fasinumab SC, including the loading dose on day 1.

Patients randomized to treatment group 3 will receive IV infusions of fasinumab (9 mg) on day 1 and week 8 for a total of 2 doses. Patients randomized to treatment groups 1, 2, or 4 will receive matching placebo to fasinumab IV.

Study drug (fasinumab or placebo) will be administered at the study site after all study visit procedures have been completed. All SC injections will be in the abdomen or thigh. At the day 1 and week 8 visits, patients will receive the SC injection first, followed by the IV infusion. After IV administration of study drug, patients will be observed in the clinic for approximately 2 hours for evidence of a hypersensitivity reaction, and for 1 hour after SC dosing. Instructions for study drug administration are provided in the pharmacy manual. Doses of study drug must be given within ± 7 days from the scheduled dose date. If the window is missed, the dose should not be administered. The next dose should be administered at the next scheduled dosing date.

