6.2.4. Baseline/Randomization Visit (Day 1)

If a patient has met all screening eligibility criteria, study sites will complete the procedures as detailed in the schedule of events for the baseline visit. The patient reported outcomes assessments at this and subsequent visits should be completed prior to all other assessments. All laboratory samples at this and subsequent visits must be collected and all study procedures must be performed before study drug is administered. At dosing study visits, urine pregnancy testing will be done and read before the study drug is administered. In the event of a positive urine pregnancy test result, the patient should have a serum pregnancy test with a negative result in order to continue study participation. If the serum pregnancy test is positive, the patient should be withdrawn from study drug and should be asked to return to the clinic for all remaining study visits per the visit schedule (see [Section 6.2.7](#)).

The date of the first dose of study drug is designated as day 1. All subsequent visits should be scheduled based on this date.

6.2.5. Weeks 1 through 16

Complete visits and assessments are outlined in the schedule of events ([Table 1](#)). The patient reported outcomes should be completed prior to all other assessments. All study procedures should be completed before administration of study drug. The last dose of study drug is administered at week 12. Patients who discontinue study drug should return for the remaining study visits, if possible. If patients are not able to continue study participation, they should return for an early termination visit, at which the treatment-period early termination visit assessments will be performed per the schedule of events.

At dosing study visits, urine pregnancy testing will be done and read before the study drug is administered. Study drug will be withheld in the event of a positive urine pregnancy test result. In the event of a positive urine pregnancy test result, a serum pregnancy test must be performed. If the serum pregnancy test is negative, the patient may continue study participation. If the serum pregnancy test is positive, the patient must be permanently discontinued from study drug and should be asked to return to the clinic for all remaining study visits per the visit schedule ([Section 6.2.7](#)).

6.2.6. Weeks 20 through 36

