5.7. Analyses of Efficacy Variables

5.7.1. Analysis of Primary Efficacy Variable(s)

The primary endpoint in the study is the change from baseline to week 16 in the average daily LBPI NRS score. The following hypotheses will be tested (with no control for multiplicity):

- H₁: No difference in the change from baseline to week 16 in the average LBPI NRS score for fasinumab 6mg SC Q4W and Placebo.
- H₂: No difference in the change from baseline to week 16 in the average LBPI NRS score for fasinumab 9mg SC Q4W and Placebo.
- H₃: No difference in the change from baseline to week 16 in the average LBPI NRS score for fasinumab 9mg IV Q8W and Placebo.

Statistical Model

The primary efficacy variable, change from baseline in LBPI score, will be analyzed using a mixed-effect model repeated measures (MMRM) approach based on the mITT. The model will include the randomization strata, baseline LBPI score, treatment, study week, and treatment-by-week interaction. Denominator degrees of freedom will be estimated using Kenward-Roger's approximation. Data from all patients, including data collected after discontinuing treatment up to the earlier of withdrawal of consent, week 16 or 5 weeks after the last dose of study drug, will be used in the primary efficacy analyses according to the intent-to-treat principle using the MMRM approach with no imputation for missing data.

The fitting of MMRM will be performed using MIXED procedure in SAS with an unstructured covariance matrix to model the within-patient errors. If the model does not converge using unstructured covariance matrix, a simpler covariance structure with fewer parameters will be

used according to the following order: heterogeneous autoregressive (1)ARH(1), Compound symmetry (CSH), Toeplitz (TOEP).

The Least-Squares means estimates for the mean change from baseline to week 16, as well as the differences of the estimates between fasinumab doses and placebo, with their corresponding standard errors, p-values and associated 95% confidence intervals will be provided from the MMRM model. The graph of LS-mean +/- SE by visit will be provided. In addition, the absolute value at week 16 and change from baseline to week 16 in LBPI NRS score will be summarized and graphed by visit.

Sample SAS codes that can be used to implement the MMRM analysis are shown below:

```
proc mixed data=LBPI_NRS;  
  class subid trt week stratum1 stratum2 stratum3;  
  model chg = baseline trt stratum1 stratum2 stratum3 week trt*week  

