5.8. Analysis of Safety Data

The analysis of safety and tolerability will be performed on the SAF, as defined in [Section 3.3](#). The safety analysis will be based on the reported AEs and other safety information (clinical

laboratory evaluations, vital signs, physical exam and 12-lead ECG). Thresholds for Potential Clinically Significant Values (PCSV) in laboratory variables, vital signs and ECG are defined in [Appendix 10.2](#).

The summary of safety results will be presented for each treatment group.

Period of observation: The observation period will be divided into three segments: pre-treatment, on-treatment, and follow-up period.

- The pre-treatment period is defined as the time from signing the ICF to before the first dose of study drug.
- The on-treatment period is defined as the day from first dose of study drug to 4 weeks after the last dose of SC study drug or 8 weeks after the last dose of IV study drug, whichever is later.
- The Post/Treatment follow-up period is defined as from the end of the on-treatment period+1 day to the end of study visit (week 36).

Unless otherwise noted, summaries of safety variables will use data from the on-treatment period. Listings of safety variables will include data from all periods and values occurring during the pre-treatment and follow-up period will be flagged in the listings.

Day 1 is the first day of investigational product, Day –1 is the day before, and there is no Day 0.

The time interval to detect any on-treatment event or abnormality is the on-treatment period. Data collected outside this interval will be excluded from the estimation of descriptive statistics and identification of abnormalities for laboratory evaluations, ECGs and vital signs. All post-baseline data during the interval will be using in the PCSV analysis including scheduled and unscheduled assessments.

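### The 5-week mITT cut ignores the IV arm's 8-week interval, so IV patients who had both infusions but no week-12 placebo injection lose their week-16 value

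*SAP*

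**What the plan says.** SAP 3.1 defines the mITT as treated patients in their randomized arm, "including data up to 5 weeks after the last dose of study drug". SAP 5.7.1 repeats the limit for the primary MMRM: data run to the earliest of consent withdrawal, "week 16 or 5 weeks after the last dose of study drug, will be used in the primary efficacy analyses". SAP 5.7.2 uses the mITT for the secondary endpoints as well. Neither section separates routes or gives a reason for 5 weeks. SAP 1.1.5, which is headed as modifications from the protocol, does not mention the cut. Protocol 9.5.2.1 had kept post-discontinuation data up to week 16.

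The protocol uses study drug for both active and placebo: "Study drug (fasinumab or placebo) will be administered at the study site" (3.1). IV-arm patients get "1 IV infusion of fasinumab on day 1 and at week 8". Protocol 5.1 confirms that these two infusions are the whole active course: "Patients randomized to treatment group 3 will receive IV infusions of fasinumab (9 mg) on day 1 and week 8 for a total of 2". Their SC dosing after day 1 is "1 SC injection of matching placebo at weeks 4, 8, and 12" (Protocol 3.1), and "The last dose of study drug is administered at week 12" (Protocol 6.2.5). The final study drug in the IV arm is therefore a placebo injection.

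Elsewhere the SAP allows IV dosing 8 weeks. The on-treatment period in SAP 5.8 ends 4 weeks after the last SC dose "or 8 weeks after the last dose of IV study drug, whichever is later". IV exposure in 5.6.2 adds 56 days to the last dose, and post-treatment adverse events in 5.8.1 start more than 56 days after the last IV dose.

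The FAS (SAP 3.2) has no such cut. It is the sensitivity set for LBPI, RMDQ and PGA (5.7.1) and the set for the exploratory analyses (5.7.3).

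**The concern.** Five weeks is the 4-week SC interval plus one week. That reading is an inference, since the SAP does not explain the figure, but it fits the SC arms. The IV arm gets no equivalent. Take two IV patients with identical active exposure, one who had the week-12 placebo injection and one who did not. The first contributes a week-16 value to the primary analysis and the second does not.

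The clinical hold makes this more than a curiosity. SAP section 1 says dosing ended before all randomized patients had finished, so some patients will have week 8 as their last dosing visit. The same section encourages patients to stay to week 36, so their week-16 data may well exist. At stake is the precision of H3, the 9 mg IV versus placebo comparison at week 16, for the primary endpoint and for RMDQ and PGA.

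**Working it through.** **Reproducing the plan's day count.** With day 1 as first dose, week w falls on day 7w + 1. Week 8 is day 57, week 12 is day 85 and week 16 is day 113. Adding ±7 to 113 gives [106, 120], the window in SAP 6.5. The week-16 value averages 6 diary days (SAP 4.4.1), which are days 107 to 112 for a day-113 visit.

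**Cut by last dosing visit.** Present cut = last dose + 35. SAP 5.8 end of treatment = later of last SC + 28 and last IV + 56. Proposed cut = last infusion + 63 (8 weeks plus 1). All patients are on schedule with no earlier dose missed.

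| Last dosing visit | Last infusion | Present cut | SAP 5.8 end | Last infusion + 63 |
|---|---|---|---|---|
| Day 1 | 1 | 36 | 57 | 64 |
| Week 4 (day 29) | 1 | 64 | 57 | 64 |
| Week 8 (day 57) | 57 | 92 | 113 | 120 |
| Week 12 (day 85) | 57 | 120 | 113 | 120 |

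- Last visit week 8: the cut is 106 − 92 = 14 days before the week-16 window opens, so 0 of 6 diary days are kept. Week 12 (day 85) is kept.
- Dose window of ±7 days (Protocol 5.1): a week-8 dose on day 50 is cut at day 85, and one on day 64 at day 99. Both precede day 106, so week 16 is always lost.
- Last visit day 1: the cut at day 36 precedes the week-8 window [50, 64], so week 8 is lost although the IV interval runs to day 57.
- A flat 8 weeks would not be enough. An infusion on day 50 would be cut at day 106 and keep 0 of 6 days. Nine weeks gives day 113 and keeps 6 of 6.

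**Numbers affected (assumed).** The documents give 563 randomized at the hold, so 563/4 = 140.75 per arm if allocation was even. Assume even accrual over T weeks before the hold and no other dropout. A share 4/T then has week 8 as last dosing visit:

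- T = 26: 140.75 × 4/26 = 21.7 per arm
- T = 52: 140.75 × 4/52 = 10.8 per arm

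The share with a usable week-16 value rises from (T − 12)/T to (T − 8)/T: 14/26 to 18/26 (54% to 69%), or 40/52 to 44/52 (77% to 85%).

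**Precision.** Counting only observed week-16 values, the SE ratios are √(14/18) = 0.882 and √(40/44) = 0.953, reductions of 12% and 5%. The MMRM recovers part of this because these patients keep weeks 2 to 12. A two-visit approximation with correlation r between weeks 12 and 16 is Var ∝ (1 − r²)/n16 + r²/n12. After the change n16 = n12, so Var ∝ 1/n12. The shares are the same in the IV and placebo arms, so the ratio carries over to the contrast.

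| T | r | Variance now | Variance after | SE ratio | SE reduction |
|---|---|---|---|---|---|
| 26 | 0.7 | 0.51/14 + 0.49/18 = 0.06365 | 1/18 = 0.05556 | 0.934 | 6.6% |
| 26 | 0.9 | 0.19/14 + 0.81/18 = 0.05857 | 0.05556 | 0.974 | 2.6% |
| 52 | 0.7 | 0.51/40 + 0.49/44 = 0.02389 | 1/44 = 0.02273 | 0.975 | 2.5% |
| 52 | 0.9 | 0.19/40 + 0.81/44 = 0.02316 | 0.02273 | 0.991 | 0.9% |

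**The case against.** - **The FAS keeps the data.** This stands in part. The SAP already plans an H3 estimate that uses these week-16 values, so they are lost only from the mITT analyses. But the FAS also keeps long off-drug follow-up, for example a week-16 value 112 days after a single day-1 infusion. No planned analysis keeps IV data to the end of the IV interval and stops there.
- **The cut falls on every arm alike.** True, because dosing is double-dummy. A reader might infer that the three dose contrasts estimate different on-treatment effects, or that H3 is biased. The documents do not show this. On schedule, a retained week-16 value normally means the patient was dosed at week 12. An SC patient is then within 4 weeks of active drug and an IV patient within 8, so both are on regimen. For patients stopped by the hold the cause is administrative, and the result is lost precision.
- **The safety rule is not a precedent for following the active route.** This stands. The later-of rule in SAP 5.8 applies to all arms, so an SC patient can be on treatment by virtue of a placebo infusion. A safety window also need not match an efficacy one. The rule shows only that the SAP recognises an 8-week IV interval elsewhere.
- **Two cuts mean two placebo data sets, chosen after two unblinded efficacy interims (SAP 7).** Both are real costs. Symmetry within the IV contrast is preserved, because placebo patients receive matching infusions.
- **H3 carries limited weight.** Also fair. The SAP tests it without multiplicity control, and Protocol 9.1 reached it only after both SC hypotheses were rejected.

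**Conclusion.** The point holds as a gap in how the efficacy cut is defined for the IV arm. An IV patient with both infusions and no week-12 placebo injection always loses week 16 from the mITT primary and secondary analyses. One dosed only on day 1 loses week 8. The day arithmetic rests on the documents alone.

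The size does not. There is no accrual curve and no count of patients last dosed at week 8. With even accrual over 26 to 52 weeks, no other dropout and r of 0.7 to 0.9, the avoidable inflation is modest: the SE of the IV contrast would fall by about 3-7% (26 weeks) or 1-2.5% (52 weeks). The documents support neither a claim that H3 is invalid nor a claim that the data leave the trial altogether. The change is worth making because it is cheap and uses follow-up that the study is already trying to collect.

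**What to change.** For the IV-versus-placebo contrast on LBPI, RMDQ and PGA, cut data in both arms at 9 weeks after the last infusion: the 8-week interval plus the one week that the present cut allows beyond the SC interval. Keep 5 weeks after the last dose for the two SC-versus-placebo contrasts. State the reason for each length in SAP 3.1 and 5.7.1, and list the departure from Protocol 9.5.2.1 in SAP 1.1.5.

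For patients on schedule this changes only those whose last dosing visit was an infusion visit: day 1 (cut moves from 36 to 64, restoring week 8) and week 8 (92 to 120, restoring week 16). Last visits at week 4 and week 12 keep their present cuts of day 64 and day 120.

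Personnel who remain blinded should specify the rule before database lock. If the single primary cut must stand because of the unblinded interims, prespecify the 9-week version as a supplementary H3 analysis.

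The cost is SAP wording, one extra model fit, and a placebo data set that differs slightly between the IV and SC contrasts.

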3.2. The Full Analysis Set (FAS)

The full analysis set (FAS) includes all randomized patients per IVRS and it is based on the treatment allocated (as randomized). The FAS will be used to perform sensitivity analysis for the primary and selected secondary endpoints.

3.3. The Safety Analysis Set (SAF)

The safety analysis set (SAF) includes all randomized patients who received any study drug; it is based on the treatment received (as treated).

Patients randomized to the ‘Placebo SC Q4W and Placebo 9mg IV Q8W’ treatment arm who receive at least one dose of active treatment will be classified in the active treatment group in the SAF. Patients randomized to any of the treatment groups receiving active fasinumab doses who wrongly receive another dose of fasinumab will be classified to the arm of the lowest dose of fasinumab received. For example a patient randomized to the ‘Fasinumab 9mg SC Q4W and placebo 9mg IV Q8W’ who wrongly receives treatment with fasinumab 6mg SC at least once will be classified under the ‘Fasinumab 6mg SC Q4W and placebo 9mg IV Q8W’ treatment arm. Treatment compliance/administration and all clinical safety variables will be analyzed using the SAF.

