9.3.2. Safety Analysis Set

The safety analysis set (SAF) includes all randomized patients who received any study drug; it is based on the treatment received (as treated). Treatment compliance/administration and all clinical safety variables will be analyzed using the SAF.

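### The safety set assigns mis-dosed active patients to the lowest fasinumab dose received, so a patient treated almost entirely at 9 mg SC can be analysed as 6 mg SC

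*SAP*

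**What the plan says.** SAP 3.3 and Protocol 9.3.2 both define the SAF as treated patients grouped by the treatment they actually received. The protocol adds no rule for dosing errors. SAP 3.3 adds two:

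- Placebo-arm patients "who receive at least one dose of active treatment will be classified in the active treatment group in the SAF".
- Active-arm patients who are wrongly given a different fasinumab dose "will be classified to the arm of the lowest dose of fasinumab received".

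The SAP's example sets the threshold for the second rule at one dose. A 9 mg SC patient who "wrongly receives treatment with fasinumab 6mg SC at least once will be classified under the" 6 mg SC arm. No rationale is given.

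The reach of the rule is wide. SAP 3.3 says that "all clinical safety variables will be analyzed using the SAF", and SAP 5.8 says: "The summary of safety results will be presented for each treatment group". SAP 5.8.3 also tabulates joint replacements by treatment group.

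**The concern.** An as-treated set should put patients where their exposure puts them. This rule lets one lower dose outweigh all the others. It also works in one direction only: a 9 mg SC patient given 6 mg once moves to the 6 mg arm, and a 6 mg patient given 9 mg once stays there. Every 6/9 mg SC error therefore ends in the 6 mg SC arm.

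At stake is the dose comparison for safety. Protocol 1.1 reports that arthropathy risk rose with dose for tanezumab, another antibody against the same target. If fasinumab behaves similarly, events in patients dosed mainly at 9 mg would be counted against 6 mg.

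There is also a gap. The 9 mg SC Q4W and 9 mg IV Q8W arms carry the same dose label, so a lowest-dose rule does not say where a patient who received both belongs.

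**Working it through.** The plan states no figure that depends on this rule, so there is none to reproduce.

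**Step 1: exposure against assigned arm.** Protocol 3.1 says that patients in the SC arms "will receive 2 SC injections of fasinumab on day 1 (SC loading dose), 1 SC injection at weeks 4, 8, and 12", and that patients in the IV arm "will receive 1 IV infusion of fasinumab on day 1 and at week 8". Planned totals are:

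- 6 mg SC: 12 + 6 + 6 + 6 = 30 mg
- 9 mg SC: 18 + 9 + 9 + 9 = 45 mg
- 9 mg IV: 9 + 9 = 18 mg

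A 9 mg SC patient with k maintenance doses wrongly given as 6 mg receives 45 − 3k mg:

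| k | Total received | Share of 9 mg SC plan | Share of 6 mg SC plan | Arm under SAP 3.3 |
|---|---|---|---|---|
| 1 | 42 mg | 93% | 140% | 6 mg SC |
| 2 | 39 mg | 87% | 130% | 6 mg SC |
| 3 | 36 mg | 80% | 120% | 6 mg SC |

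With one error the patient is 3 mg from the 9 mg plan and 12 mg from the 6 mg plan. In the other direction, a 6 mg patient with one 9 mg maintenance dose receives 33 mg (110% of the 6 mg plan), so staying in the 6 mg arm is reasonable.

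An IV-arm patient who received both infusions and one active 6 mg SC injection in error has 18 + 6 = 24 mg, of which 18 mg was IV, yet the rule reads as sending that patient to 6 mg SC.

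**Step 2: effect on the 9-versus-6 mg contrast.** SAP 1 gives 563 patients randomized, so 563/4 = 140.75, or about 141 per arm (actual SAF arm sizes are not given). Let m patients with 9 mg-level risk p9 be added to n = 141 patients with risk p6.

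- Observed 6 mg rate = (n·p6 + m·p9)/(n + m)
- Observed difference = p9 − observed 6 mg rate = (p9 − p6)·n/(n + m)
- Proportional shrinkage = m/(n + m)

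With m assumed from 1 to 14 (about 1% to 10% of an arm), and p6 = 1% and p9 = 3% assumed for the risk ratio:

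| m | Shrinkage of risk difference | Risk ratio (true value 3.00) |
|---|---|---|
| 1 | 1/142 = 0.7% | 2.96 |
| 3 | 3/144 = 2.1% | 2.88 |
| 7 | 7/148 = 4.7% | 2.74 |
| 14 | 14/155 = 9.0% | 2.54 |

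**Step 3: one rare event.** Take hypothetical counts of 3/141 at 9 mg and 1/141 at 6 mg, a risk ratio of 3.0. Moving one patient who had an event gives 2/140 and 2/142, a ratio of 1.01. This needs a dosing error and an event in the same patient. At an assumed 3% event rate, the expected number of moved events is 1.41 × 0.03 = 0.04 if 1% of the arm is mis-dosed, and 14.1 × 0.03 = 0.42 if 10% is.

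**The case against.** The strongest reply is that this is a small matter. Study drug is given at the site from coded kits, so errors should be few. The safety analyses are descriptive, with no test or decision rule attached. Protocol 9.4 already plans a listing of patients not treated as randomized, and SAP 5.8.1 lists patients with AESIs, serious events and deaths. All of that stands and limits the size. It does not remove the defect. The Protocol 9.4 listing is not repeated in SAP 5.5, neither listing ties an event to the dose being received at onset, and the SAP plans no safety table under another assignment.

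Four stronger readings are tempting, and the documents do not support them.

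- **That the rule makes 9 mg look safer.** If errors are unrelated to risk, removing mis-dosed patients lowers the 9 mg numerator and denominator together and leaves its expected rate unchanged. The narrowing comes from the 6 mg side.
- **That it bears on the clinical hold.** SAP 1 describes the osteoarthritis studies as limited to 6 mg SC Q8W. Both SC arms here exceed that, so moving a patient between them does not touch the issue. Nor do the documents give a class-wide dose relation: the one in Protocol 1.1 is for tanezumab.
- **That it contradicts the placebo rule.** The placebo rule separates exposed from unexposed patients; the active rule ranks fasinumab doses only. They answer different questions.
- **That assigning to the highest dose would cure it.** A 6 mg patient with one 9 mg dose would then enter the 9 mg arm, diluting the contrast from the other side.

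**Conclusion.** The point holds in a limited form. Followed exactly, SAP 3.3 misclassifies patients by its own as-treated standard: one 6 mg dose overrides a record that is 93% of the 9 mg SC plan. Where risk rises with dose, the 9-versus-6 mg risk difference shrinks by about 0.7% for one such patient and 4.7% for seven. These figures assume about 141 patients per arm, moved patients who carry 9 mg-level risk, and errors unrelated to risk; the number of errors is unknown. Pooled fasinumab versus placebo does not change, because the rule only moves patients between active arms.

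For common adverse events this is negligible. It deserves correction because adjudicated arthropathy and joint replacement are rare enough for one moved event to change an arm comparison, and because errors between 9 mg SC and 9 mg IV have no defined home.

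**What to change.** In SAP 3.3, replace the lowest-dose rule for active-arm patients. Assign each mis-dosed patient to the arm that matches the dose and route of the majority of active doses received, or as randomized if tied. State that the loading dose counts as one dose, in line with the compliance convention in SAP 5.6.1. This settles SC-versus-IV errors as well.

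Carry the Protocol 9.4 listing of patients not treated as randomized into the SAP. For each such patient show the doses received, any AESI or joint replacement, and the dose being received at event onset.

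The cost is a few sentences and one listing, with no new data. The downside is small: a patient with a minority of erroneous doses stays in the main-dose arm, and the listing makes that visible.
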